#### **6.6.8. Performance Status**

The ECOG shift from baseline to the highest score during the post-baseline period will be summarized by treatment arm.

CCI

## **7. INTERIM ANALYSES**

### **7.1. Introduction**

The goals of the interim analyses are to allow early stopping of the study for futility or efficacy. The interim analysis of OS will be performed as described in [Section 5.1.1](#) and [5.1.2](#) using the methodology described in [Section 6.2.1](#) for OS.

The interim analysis will be performed by an independent statistician. Unblinded results from the interim analysis will not be communicated to the Sponsor's clinical team or to any party involved in the study conduct (apart from the independent statistician and E-DMC members) until the E-DMC has determined that (i) OS analysis has crossed the prespecified boundary (except for the efficacy boundary at the first planned interim analysis for the intensive chemotherapy study when there is no plan to stop for efficacy regardless of whether the boundary is crossed) and the Sponsor has decided to terminate the study or (ii) the study needs to be terminated due to any other cause, including safety reasons. Further details will be described in the E-DMC charter.

The final OS analysis will be performed by the Sponsor's clinical team.

## 7.2. Interim Analyses and Summaries

At each analysis timepoint, the critical boundaries for the group sequential test will be derived from the predefined spending function(s) as described in [Section 5.1](#). The calculations of boundaries will be performed using EAST. For the intensive chemotherapy study, there will not be any efficacy stopping at the first planned interim analysis even if the efficacy stopping boundary is crossed.

Let  $l(t_1)$  and  $u(t_F)$  denote the lower critical boundaries for futility at the interim analysis and the upper critical boundaries for efficacy at the final analysis based on the test statistics  $Z_1$  and  $Z_F$ , respectively.

The critical values  $l(t_1)$  for the interim analysis of OS are determined such that

$$P_a(Z_1 \leq l(t_1)) = \beta(t_1)$$

where  $P_a$  denote the probabilities under the alternative hypothesis and  $\beta(t_1)$  denote the  $\beta$  spent, based on the predefined spending functions at information fraction  $t_1$  ( $t_1$  is calculated as the ratio of the number of deaths observed at the time of the data cutoff for the interim analysis and the total number of deaths targeted for the final analysis).

The boundary for the final efficacy analysis is derived such that

$$P_0(Z_F \geq u(t_F)) = 0.025$$

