### 5.1.2. Decision Rules

The interim analyses will be performed based on the FA set for the intensive and non-intensive chemotherapy populations separately and independently of each other as described in the following. The key secondary Fatigue endpoint will be analyzed using a hierarchical testing procedure, provided the primary OS endpoint is statistically significant favoring the experimental arm within each patient population (intensive and/or non-intensive).

An interim analysis will not be performed for the China subset. Full analysis following early stopping at an interim analysis or following final analysis will be carried out for the China subset based on the specifications in other sections.

Non-binding for the futility implies that the futility boundary will be constructed in such a way that it can be overruled if desired by the external data monitoring committee (E-DMC) without inflating the type-1 error rate and without decreasing the power.

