#### Intensive Chemotherapy Study:

Two interim analyses are planned. One efficacy and futility interim analysis is planned when 50% of death events have occurred in the intensive chemotherapy population. However, no efficacy stopping will be made even if the interim analysis result crosses the efficacy boundary. A second interim analysis of efficacy and futility is planned when 70% of death events have occurred or upon completion of enrollment of the intensive chemotherapy population, whichever is later. An O'Brien-Fleming boundary with Lan-DeMets spending function will be used for efficacy and a Rho(3)  $\beta$ -spending function will be used for the non-binding futility boundary. If exactly 50% of the events is accrued at the first interim analysis, the futility boundary will be crossed when 1-sided  $p > 0.461$ . If exactly 70% of the events is accrued at the second interim analysis, the futility boundary will be crossed when 1-sided  $p > 0.186$  and the efficacy boundary will be crossed when 1-sided  $p < 0.007$ . If the actual number of events at the interim analyses is different, the corresponding spending function will be used to calculate the actual stopping boundaries. A 1-sided  $p < 0.023$  at the final analysis suggests the null hypothesis is to be rejected.

**Table 2. Planned Stopping Boundaries for Overall Survival at Interim Analyses and Final Analysis for the Intensive Chemotherapy Study**

Analysis	Number of Events (%)	Cumulative Alpha Spent	Cumulative Beta Spent	Futility Boundary p-value	Efficacy Boundary p-value
First IA	134 (50%)	0.002	0.013	0.461	*
Second IA	187 (70%)	0.007	0.034	0.186	0.007
FA	267 (100%)	0.025	0.100	0.023	0.023

Abbreviations: IA=interim analysis; FA=final analysis

The cumulative alpha spent, cumulative beta spent, and boundaries were calculated using software EAST (version 6.4).

\* No stopping for efficacy regardless whether the efficacy boundary is crossed or not.

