## Non-intensive Chemotherapy Study:

One interim analysis is planned. An interim analysis of efficacy and futility is planned when 60% of death events have occurred or upon completion of enrollment of the non-intensive chemotherapy population, whichever is later. An O'Brien-Fleming boundary with Lan-DeMets spending function will be used for efficacy and a Rho(3)  $\beta$ -spending function will be used for the non-binding futility boundary. If exactly 60% of the events is accrued at the interim analysis, the futility boundary will be crossed when 1-sided  $p > 0.302$  and the efficacy boundary will be crossed when 1-sided  $p < 0.004$ . If the actual number of events at the interim analyses is different, the corresponding spending function will be used to calculate the actual stopping boundaries. A 1-sided  $p < 0.024$  at the final analysis suggests the null hypothesis is to be rejected.

**Table 3. Planned Stopping Boundaries for Overall Survival at Interim Analyses and Final Analysis for the Non-Intensive Chemotherapy Study**

Analysis	Number of Events (%)	Cumulative Alpha Spent	Cumulative Beta Spent	Futility Boundary p-value	Efficacy Boundary p-value
IA	132 (60%)	0.004	0.021	0.302	0.004
FA	220 (100%)	0.025	0.100	0.024	0.024

Abbreviations: IA=interim analysis; FA=final analysis

The cumulative alpha spent, cumulative beta spent, and boundaries were calculated using software EAST (version 6.4).

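### The final-boundary equation in SAP 7.2 ignores the alpha spent at the efficacy interim and does not match the final thresholds of 0.023 and 0.024 in SAP 5.1.2

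*SAP*

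**What the plan says.** SAP 7.2 opens by saying that, at each analysis, "the critical boundaries for the group sequential test will be derived from the predefined spending function(s) as described in" Section 5.1, with the calculation done in EAST. It then defines two symbols: a futility boundary at the interim and an efficacy boundary at the final analysis. It gives no symbol or equation for an efficacy boundary at the interim. For the final look it states "The boundary for the final efficacy analysis is derived such that" and then "P_0(Z_F \geq u(t_F)) = 0.025".

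SAP 5.1.2 sets the operating rules. Both studies use Lan-DeMets O'Brien-Fleming spending at an overall 1-sided 0.025.
- **Intensive study:** looks at 134, 187 and 267 deaths. The first interim cannot stop the study for efficacy. The second can, at p<0.007. A 1-sided p<0.023 "at the final analysis suggests the null hypothesis is to be rejected".
- **Non-intensive study:** looks at 132 and 220 deaths, with efficacy stopping at p<0.004 at the interim and rejection at p<0.024 at the final.

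Table 2 ("Planned Stopping Boundaries for Overall Survival at Interim Analyses and Final Analysis for the Intensive Chemotherapy Study") and Table 3 ("Planned Stopping Boundaries for Overall Survival at Interim Analyses and Final Analysis for the Non-Intensive Chemotherapy Study") repeat these values. In both tables 0.025 is the cumulative alpha in the final row. Futility is non-binding: 5.1.2 says "it can be overruled if desired by the external data monitoring committee (E-DMC) without inflating the type-1 error rate". Protocol 9.3.1 requires the overall level to be preserved at 1-sided 0.025 across the interim and final analyses.

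**The concern.** The equation in 7.2 is a marginal probability. It would be right if the interim could stop the study only for futility, but each study has an interim that can stop it for efficacy. Spending alpha there and then testing at the full 0.025 at the end exceeds the overall level. Overall survival is the primary endpoint of both registration trials, and the fatigue test is reached only if it succeeds, so the final rule should be written correctly wherever it appears.

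The equation is also the only formula in the SAP for the final boundary. The printed 0.023 and 0.024 hold at the planned looks. The efficacy interim may fall later, because it waits for enrollment to finish if that comes after the event target, and SAP Section 2 allows the final event count to differ after data cleaning. The recalculation sentences in 5.1.2 mention only the interim analyses. An analyst who needs a new final boundary may therefore turn to 7.2.

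**Working it through.** **Inputs.** Overall 1-sided alpha 0.025, the spending function and the event counts come from SAP 5.1.2 and Tables 2 and 3. Futility is ignored because it is non-binding. Spending: α(t) = 2[1 − Φ(2.2414/√t)], where t is the fraction of final events and 2.2414 is the normal quantile at 0.9875. The correlation between looks i<j is √(t_i/t_j).

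**Step 1: reproduce the plan's figures.** Each boundary is solved so that the cumulative crossing probability under the null equals α(t).

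| Study | Deaths | Cumulative alpha | Boundary z | Nominal p | SAP prints |
|---|---|---|---|---|---|
| Intensive | 134 | 0.0016 | 2.956 | 0.0016 | no efficacy stop |
| Intensive | 187 | 0.0074 | 2.462 | 0.0069 | 0.007 |
| Intensive | 267 | 0.0250 | 2.002 | 0.0226 | 0.023 |
| Non-intensive | 132 | 0.0038 | 2.669 | 0.0038 | 0.004 |
| Non-intensive | 220 | 0.0250 | 1.981 | 0.0238 | 0.024 |

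The tabulated thresholds reproduce to three decimals. The intensive values count the first-interim boundary in the calculation, although it triggers no stop.

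**Step 2: solve the 7.2 equation as printed.** P0(Z_F ≥ u) = 0.025 gives u = 1.960 and p = 0.025 in both studies.

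**Step 3: overall type I error, P0(Z_IA ≥ u_IA or Z_F ≥ u_F), stopping only at the interim that can stop for efficacy.**

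| Final rule | Intensive | Non-intensive |
|---|---|---|
| 7.2 equation, u_F = 1.960 | 0.0269 | 0.0262 |
| Unrounded spending boundaries | 0.0247 | 0.0250 |
| Printed thresholds (0.007 then 0.023; 0.004 then 0.024) | 0.0250 | 0.0253 |

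The excess over 0.025 under the literal equation is 0.0269 − 0.0250 = 0.0019 and 0.0262 − 0.0250 = 0.0012. The third row exceeds 0.025 slightly in the non-intensive study only because the printed thresholds are rounded up.

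**Step 4: results affected.** With 1:1 allocation, the observed hazard ratio at a threshold is about exp(−2z/√D).
- D = 267: 0.783 at p = 0.023 and 0.787 at p = 0.025.
- D = 220: 0.766 at p = 0.024 and 0.768 at p = 0.025.

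The chance of reaching the final analysis and landing between the printed threshold and 0.025 is 0.19% (intensive) and 0.10% (non-intensive) under the null. Under the design hazard ratios of 0.67 and 0.64 it is 0.57% and 0.27%.

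**Step 5: a later interim (illustration).** The timing is assumed, with a single efficacy interim. At 75% of events the correct final p is 0.0221 and literal use gives an overall 0.0276. At 80% the figures are 0.0214 and 0.0280.

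**The case against.** The strongest reply is that nobody has to solve this equation. The section headed as decision rules states 0.023 and 0.024, Tables 2 and 3 repeat them and label 0.025 as cumulative, and 7.2 itself begins by deferring to the spending functions and to EAST. The interim efficacy boundaries missing from 7.2 are in 5.1.2. The disputed band is narrow. All of this stands, and it limits the weight of the point.

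A reader might go further and infer that the SAP prints two rival p-value thresholds for the final test. It does not: 7.2 prints an equation, and the 0.025 threshold appears only when that equation is solved in isolation. A reader might also infer that the design fails to control type I error. The documents do not support that either, since the tabulated boundaries reproduce and control the error to within rounding.

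The reply does not make the equation right. Taking 0.025 as the probability of first crossing at the final analysis is worse: added to the interim crossing probability, it gives an overall 0.0324 (intensive, counting only the interim at 187 deaths) and 0.0288 (non-intensive). Crediting futility stopping is not open, because that boundary is non-binding.

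**Conclusion.** The equation in SAP 7.2 is wrong as written, because it uses the cumulative alpha as the marginal tail at the final analysis. It implies a threshold of 0.025 where the correct values are 0.0226 and 0.0238, printed as 0.023 and 0.024. Applied literally, it would raise the overall 1-sided error by about 0.002 (intensive) and 0.001 (non-intensive). The governing rule can be recovered from the rest of the SAP, so this is an inconsistency that should be corrected, with small practical risk.

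The figures assume normally distributed log-rank statistics with independent increments, looks at exactly the planned event counts, futility ignored, and no efficacy stop at the first intensive interim.

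**What to change.** Before unblinding, delete the equation and its lead-in. Refer instead to SAP 5.1.2 and Tables 2 and 3, and state that the final boundary is recalculated in EAST from the Lan-DeMets O'Brien-Fleming spending function at the actual interim and final event counts.

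If a formula is kept, write it as P0(crossing the efficacy boundary at any look, including the final) = 0.025. Say explicitly that in the intensive study the first-interim boundary counts in this calculation although it triggers no stop; this reproduces 0.0226. Without that statement a new mismatch is possible. Assigning the remaining alpha, 0.025 − 0.0074 = 0.0176, to the final look while conditioning only on no crossing at the second interim gives u = 2.005 and p = 0.0225 (0.02246 unrounded, so 0.022 to three decimals), which does not match Table 2.

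The cost is one or two sentences of SAP text. Events, sample size and Tables 2 and 3 do not change.

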## 9. APPENDIX

### 9.1. Note on Defining CIR for “Fatigue” Single-item from the MDASI AML/MDS Questionnaire

*(Note this description is for the cohort of intensive patients. The analysis for non-intensive patients can easily be inferred by extending Week 8 to Week 12 throughout).*

FDA document “*Guidance for Industry. Patient-Reported Outcome Measures: Use in Medical Product Development to Support Labeling Claims*” gives following definition for Clinically Important Responder (CIR) Definition:

*“Responder definition — A score change in a measure, experienced by an individual patient over a predetermined time period that has been demonstrated in the target population to have a significant treatment benefit.”*

In the guidance the following algorithm is proposed to define responder definition: “...anchor-based approach to defining responders makes use of patient ratings of change administered at different periods of time or upon exit from a clinical trial. These numerical ratings range from **worse** to **the same** and **better**. The difference in the PRO score for persons who rate their condition the same and better or worse can be used to define responders to treatment. Patient ratings of change are less useful as anchors when patients are not blinded to treatment assignment...”

First, we do not have simple numerical rating scale with just 3 categories – that is, “numerical ratings range from **worse** to **the same** and **better**.” PGIS is used to create a simplified numerical rating with 3 categories **worse, the same, and better**.

Specifically, we create a new anchor Subject Global Impression of Change using PGIS (SGIC-S) by using the following algorithm (note that Y in below represents “Week 1”, “Week 2”,... “Week 8”):

- a. SGIC-S = -1, if PGIS at Week Y minus PGIS at baseline (day 1) is positive (this means worse);
- b. SGIC-S = 0, if PGIS at Week Y minus PGIS at baseline (day 1) is zero (ie, no change, this means the same);
- c. SGIC-S = 1, if PGIS at Week Y minus PGIS at baseline (day 1) is negative (this means better).

A repeated measures model will be used to determine CIR. [Figure 1](#) represents the SAS implementation of the model. We use the change in the “Fatigue” single-item (from baseline) as the outcome (variable changeFatigue) and SGIC-S score as the anchor variable (note that variable SGICS has only 3 categories **worse** [value of -1], **the same** [value of 0], and **better** [value of 1]). It is important to note that we treat SGIC-S in this model as a continuous variable – by doing so we impose a linear relationship between change in a “Fatigue” single-item and SGIC-S. As a sensitivity analysis we may also perform modeling using SGIC-S as a categorical variable – this approach does not impose any functional

relationship between outcome and anchor (see [figure 2](#) for SAS implementation). In this case, the larger difference between two contiguous categories (no change vs. worse, or better vs. no change) will be used as the CIR. We should note that all available post-baseline data will be used (starting with Week 1 and up to Week 8 from the cohort of intensive patients).

**Figure 1. SAS Proc Mixed code (SGIC-S as a continuous anchor)**

```
Proc mixed data=_mixed_;

  Class PID Week ;
  Model changeFatigue = SGICS / ddfm=kr s;

  Repeated Week / Type=SP(POW)(cVisit) Subject=PID;

  Estimate "CIR (One Category Change)" SGICS 1 /cl;

  Estimate "worse SGIC=-1" Intercept 1 SGICS -1 /cl;
  Estimate "the same SGIC=0 " Intercept 1 SGICS 0 /cl;
  Estimate "better SGIC=1 " Intercept 1 SGICS 1 /cl;

  Run;
```

**Figure 2. SAS Proc Mixed code (SGIC as a categorical anchor)**

```
Title "Experience Domain Score";
Proc mixed data=_mixed_;

  Class PID Week SGICS;
  Model changeFatigue = SGICS / ddfm=kr s;
  Repeated Week / Type=SP(POW)(cVisit) Subject=PID;
  LSMeans SGICS / diff cl;

  Run;
```

In addition, sensitivity analyses the above approach is augmented by using PGIC. Specifically, we create another anchor Subject Global Impression of Change using PGIC (SGIC-C) by using following algorithm (note that Y in below represents “Week 1”, “Week 2”,... “Week 8”):

- a. SGIC-C = -1, if PGIC at Week Y represents worsening (PGIC scores of 5, 6, and 7; this means *worse*);
- b. SGIC-C = 0, if PGIC at Week Y is 4 (ie, no change, this means *the same*);
- c. SGIC-C = 1, if PGIC at Week Y represents improvement (PGIC scores of 1, 2, and 3; this means *better*).

The same models represented by [figures 1](#) and [2](#) will be used (the variable SGICS will be replaced by variable SGICC representing SGIC-C).
